7.1.1 Molecular pre-screening

Not applicable.

7.1.2 Screening

Written informed consent must be obtained before any study specific medical procedures are performed. All screening/baseline assessments (with the exception of Bone Marrow Aspirates) should occur within 21 days before Week 1 Day 1.

The screening visit window for bone marrow assessments is 56 days prior to Week 1 Day 1. Should bone marrow assessments have been performed before the main informed consent is signed but within 56 days of Week 1 Day 1, no further bone marrow sampling will be required at screening. At end of treatment, a bone marrow exploratory aspirate and/or biopsy must be collected even if the screening/baseline bone marrow exploratory aspirate and/or biopsy samples were not collected. During the screening visit, inclusion and exclusion criteria will be assessed. Screening assessments to confirm eligibility must be performed prior to randomization. The results of the real time quantitative polymerase chain reaction (RQ-PCR) and the bone marrow aspirate must be available prior to randomization and first dose of study treatment.

For details of assessments required during screening please refer to [Table 7-1](#).

Laboratory baseline assessments (including hematology, chemistry, coagulation and serum pregnancy test), physical examination including extramedullary involvement, performance status, ECG, height, weight and vital signs, evaluation of all relevant medical history including cardiovascular risk factors, CML disease history, including prior TKI therapy and antineoplastic medication and prior and concomitant medication must be performed prior to the first dose of study treatment. Patients with potassium, and/or magnesium and/or total calcium levels that are < LLN at screening, must have their potassium, and/or magnesium, and/or calcium replenished through supplementation and the levels must be within normal limits prior to the first dose of study drug.

A patient who has a laboratory test (peripheral blood test) results that do not satisfy the entrance criteria may have the tests repeated. These tests may be repeated as soon as the investigator believes the re-test results are likely to be within the acceptable range to satisfy the entrance criteria, but should be completed within approximately 2 weeks of the original screening visit date. In this case, the subject will not be required to sign another Informed Consent Form (ICF), and the original patient ID number assigned by the investigator will be used. In the event that the laboratory tests cannot be performed within the screening visit window, or the re-tests do not meet the entrance criteria, or other eligibility criteria have changed and are not met anymore, the patient is considered a screen failure, and must be discontinued from the study.

A new ICF will need to be signed if the investigator chooses to re-screen the patient after a patient has screen failed, however, the patient ID number will remain the same. All required screening activities must be performed when the patient is re-screened for participation in the study. No further bone marrow sampling will be done at re-screening if a previous assessment was done within 56 days of Week 1 Day 1. After 56 days, new bone marrow biopsy and aspirates samples for cytogenetic assessment and exploratory biomarker purpose should be re-

collected at the time of the bone marrow assessment. An individual patient may be re-screened up to three times for the study. Once the number of patients screened and enrolled is likely to ensure target enrollment, the Sponsor may close the study to further screening. In this case, the patients who screen failed will not be permitted to re-screen.

7.1.2.1 Eligibility screening

Following registering in the IRT for screening, patient eligibility will be checked once all screening procedures are completed. The eligibility check will be managed via IRT system. Please refer and comply with detailed guidelines in the IRT manual.

7.1.2.2 Conditions to be fulfilled for asciminib switch

The eligibility assessments of patients who are candidates for asciminib switch will start with the bosutinib EOT visit. Assessments conducted during the EOT visit will be used to evaluate if all conditions for asciminib switch are fulfilled and there are no conditions preventing patients from receiving asciminib treatment. Therefore all efforts **MUST** be made to ensure that all EOT assessments are completed per [Table 7-1](#). In the event that all EOT assessments cannot be completed during the EOT visit, they must be completed within 42 days (6 weeks) after the bosutinib EOT visit. For details of assessments required for patients that switch treatment from bosutinib to asciminib, please refer to [Table 7-2](#). The maximum allowed time frame for patients failing bosutinib to start treatment with asciminib is 42 days after bosutinib EOT.

In case a patient presents with a grade 3 or 4 adverse event at the time of the EOT visit or develops it after the EOT visit, the adverse event must be resolved to grade 2 or lower before starting asciminib treatment and within 28 days of the date of occurrence of the adverse event as outlined in the criteria listed below.

However, a patient who has laboratory test (peripheral blood test) results or ECG results that do not satisfy the treatment switch conditions may have the tests repeated multiple times during the treatment switch screening period. The last test performed before start of asciminib dosing must meet the conditions for treatment switch as listed below.

If a patient does not meet the conditions for treatment switch, they should enter the survival follow-up phase.

The conditions for treatment switch will be checked via the IRT system. Please refer and comply with detailed guidelines in the IRT manual.

Conditions to fulfill to allow the switch to asciminib:

1. Failure to bosutinib treatment up to 96 weeks after the last patient received the first dose (adapted from the 2013 ELN Guidelines; [Baccarani et al 2013](#)). Patients must meet at least 1 of the following criteria. Failure is defined as follows:
 - Three months after the initiation of therapy or thereafter: No CHR or > 95% Ph+ metaphases.
 - Six months after the initiation of therapy or thereafter: BCR-ABL1 ratio > 10% IS and/or > 65% Ph+ metaphases.
 - Twelve months after initiation of therapy or thereafter: BCR-ABL1 ratio > 10% IS and/or > 35% Ph+ metaphases.

- At any time after the initiation of therapy, loss of CHR, CCyR or PCyR.
- At any time after the initiation of therapy, detection of new BCR-ABL1 mutations which potentially cause resistance to study treatment (asciminib or bosutinib).
- At any time after the initiation of therapy, confirmed loss of MMR in 2 consecutive tests.
- At any time after the initiation of therapy, new clonal chromosome abnormalities in Ph+ cells: CCA/Ph+.

Conditions preventing patients to switch to asciminib

- Any Grade 3 or 4 toxicity which has not resolved to Grade 2 or lower within 28 days and before starting asciminib treatment.
- Asymptomatic (Grade 2) pancreatitis if not resolved within 28 days
- Disease progression while on bosutinib treatment. The following events are considered disease progression:
 - Accelerated phase (AP) as defined by any of the following:
 - $\geq 15\%$ blasts in the peripheral blood or bone marrow aspirate, but $< 30\%$ blasts in both the peripheral blood and bone marrow aspirate.
 - $\geq 30\%$ blasts plus promyelocytes in peripheral blood or bone marrow aspirate.
 - $\geq 20\%$ basophils in the peripheral blood.
 - Thrombocytopenia ($< 100 \times 10^9/L$) that is unrelated to therapy.
 - Blast crisis (BC) as defined by any of the following:
 - $\geq 30\%$ blasts in peripheral blood or bone marrow aspirate
 - Appearance of extramedullary involvement other than hepatosplenomegaly proven by biopsy (i.e. chloroma).
- QTcF at time of switch > 480 msec or inability to determine QTc interval

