4.1.1 Study treatment switch from bosutinib to asciminib

Patients with documented treatment failure (as per the 2013 ELN guidelines; [Baccarani et al 2013](#)) while on bosutinib treatment will have the option to switch to asciminib treatment within 96 weeks after the last patient has been randomized on study. The patients who switch to asciminib will be able to receive asciminib up to end of study treatment period. At the end of the treatment period for patients who, in the opinion of the investigator still derive clinical benefit, asciminib treatment will be made available through alternative options including, but not limited to, an expanded access/compassionate use/managed access program or access to commercial supplies in applicable countries. Discontinuation of asciminib for patients who have switched over from bosutinib must follow the guidelines provided in [Section 7.1.6](#). Eligibility criteria for patients switching to asciminib are described in [Section 7.1](#).

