7.1.6 Discontinuation of study treatment

Patients may voluntarily discontinue from the study treatment for any reason at any time. If a patient decides to discontinue from the study treatment, the investigator should make a reasonable effort (e.g. telephone, e-mail, letter) to understand the primary reason for this decision and record this information in the patient’s chart and on the appropriate eCRF pages. They may be considered withdrawn if they state an intention to withdraw, fail to return for visits, or become lost to follow-up for any other reason.

The investigator should discontinue study treatment for a given patient if, he/she believes that continuation would be detrimental to the patient’s well-being. Patients who discontinue study treatment should undergo an end of treatment visit.

For patients who discontinue treatment in treatment period or switch treatment period for reasons other than death, lost to follow-up, or withdrawal of consent, the patient should enter the survival follow-up phase. Survival visit assessments (survival, antineoplastic therapies, stem cell transplant and progression) should be performed every 12 weeks until documented death, lost to follow-up, withdrawal of consent or until the end of the study. This visit can be conducted by telephone.

Patients who discontinue the study treatment for an adverse event suspected to be related to study drug or an abnormal laboratory value suspected to be related to study drug must be followed as described in [Section 8](#)

Patients may also be discontinued from the study treatment if any of the following occurs:

- discovery of patient ineligibility
- errors in treatment compliance [study treatment, other prescribed or non-prescribed medications]
- missed/unscheduled/off schedule/incomplete/incorrect assessments
- major protocol deviation
- use of prohibited treatment refer to [Section 14-Appendices](#)
- any other protocol deviation that results in a significant risk to the patient’s safety

In addition to the general discontinuation criteria, the following study specific criteria will also require discontinuation of study treatment:

- In the event of detection of T315I or V299L mutations at any time the patient **must** be discontinued from the study treatment.
- In the event of a pregnancy during study, if a patient wants to pursue the pregnancy then patient **must** be discontinued from the study treatment. However, in the event of a

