spontaneous miscarriage or in the event of elective abortion, the patient is permitted to continue study treatment.

- In the event of treatment failure the patient must be discontinued from the study treatment. Patients randomized to bosutinib treatment experiencing treatment failure may switch to asciminib treatment. The following events will constitute ‘treatment failure’, and are based on the ELN criteria ([Baccarani et al 2013](#)) defining failure of a second line treatment:
 - No CHR or > 95% Ph+ metaphases at three months after initiation of therapy or thereafter
 - BCR-ABL1 ratio > 10% IS and/or > 65% Ph+ metaphases at six months after initiation of therapy or thereafter
 - BCR-ABL1 ratio > 10% IS and/or > 35% Ph+ metaphases at 12 months after initiation of therapy or thereafter
 - Loss of CHR, CCyR or PCyR at any time after initiation of therapy
 - Detection of new BCR-ABL1 mutations which potentially cause resistance to study treatment (asciminib or bosutinib) at any time after initiation of therapy
 - Confirmed loss of MMR in 2 consecutive tests ([Section 7.2.1.1](#))
 - New clonal chromosome abnormalities in Ph+ cells: CCA/Ph+: at any time after initiation of therapy
- In the event of disease progression the patient must be discontinued from the study treatment. The following events are considered disease progression.
 1. CML-related death (any death during treatment or follow-up if the principal cause of death is marked as “study indication” in the eCRF by the investigator, or if the death occurred subsequent to documented progression to AP/BC and the cause of death is reported as “unknown” or not reported by the investigator)
 2. Accelerated phase (AP) as defined by any of the following:
 - $\geq 15\%$ blasts in the peripheral blood or bone marrow aspirate, but $< 30\%$ blasts in both the peripheral blood and bone marrow aspirate
 - $\geq 30\%$ blasts plus promyelocytes in peripheral blood or bone marrow aspirate
 - $\geq 20\%$ basophils in the peripheral blood
 - Thrombocytopenia ($< 100 \times 10^9/L$) that is unrelated to therapy
 3. Blast crisis (BC) as defined by any of the following:
 - $\geq 30\%$ blasts in peripheral blood or bone marrow aspirate
 - Appearance of extramedullary involvement other than hepatosplenomegaly proven by biopsy (i.e., chloroma).

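### The asciminib switch rules let a newly detected T315I mutation qualify a bosutinib patient for a dose that the protocol elsewhere reserves for patients without T315I

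*Combined protocol and SAP*

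**What the plan says.** On qualifying for the switch, section 7.1.2.2 states: "Patients must meet at least 1 of the following criteria". The list includes "detection of new BCR-ABL1 mutations which potentially cause resistance to study treatment (asciminib or bosutinib"). The protocol summary repeats this, and the text is the same in both protocol versions in the file. Four conditions prevent the switch: unresolved Grade 3 or 4 toxicity, unresolved Grade 2 pancreatitis, progression to accelerated phase or blast crisis, and a QTcF that is above 480 msec or cannot be determined. Conditions are checked through the IRT, whose manual is not in the documents.

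On stopping, section 7.1.6 has a rule that begins "In the event of detection of T315I or V299L mutations at any time the patient" and continues that discontinuation from study treatment is mandatory. The same section says: "Patients randomized to bosutinib treatment experiencing treatment failure may switch to asciminib treatment". Section 4.1.1 adds: "Discontinuation of asciminib for patients who have switched over from bosutinib must follow the guidelines provided in" section 7.1.6.

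On dose, section 2.3 says that 40 mg BID is currently recommended for patients without T315I, that dosing for T315I is still being studied, and that T315I patients are excluded from this trial for that reason. Exclusion criterion 1 in section 5.3 applies this to mutations known before study entry.

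**The concern.** The entry criteria and the switch criteria lead to the same drug at the same dose, but only the entry criteria keep out known T315I. The switch list has no equivalent bar, and its mutation criterion goes further: it turns a new T315I into a sufficient reason to start asciminib.

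A patient handled strictly by 7.1.2.2 could start asciminib 40 mg BID and then have to stop under 7.1.6. That costs time on a dose that the sponsor's own rationale says is not meant for that patient, in someone with at least three prior TKIs and few remaining options. It would also put patients outside the dose recommendation into the Switch Analysis Set, which section 10.1.6 uses for switch-phase safety and exploratory efficacy.

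**Working it through.** The plan states no figure to reproduce. The check is whether the rules agree when applied in order to one patient: randomized to bosutinib, no known T315I at entry, T315I first detected on treatment.

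1. **Is the mutation of the qualifying kind?** Sections 1.2.2 and 2.5 say bosutinib has no activity against T315I. It is therefore a new mutation potentially resistant to one of the two study drugs, and the 7.1.2.2 criterion is met.
2. **Is one criterion enough?** Yes, by the wording of 7.1.2.2.
3. **Does a preventing condition apply?** There are 4 conditions (toxicity, pancreatitis, progression, QTcF), and 0 of the 4 concern a mutation. The switch is allowed.
4. **Does another rule forbid it?** Section 7.1.6 requires study treatment to stop on T315I at any time, and 4.1.1 brings asciminib after the switch under 7.1.6. Section 2.3 independently says the dose is for patients without T315I.

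Steps 1 to 3 say the patient may start; step 4 says the patient must stop. Step 3 also applies to a patient who qualifies on another criterion, such as BCR-ABL1 above 10% at six months, and is found to carry T315I at end of treatment: again no listed condition prevents the switch.

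Table 7-2 does have a mutation-status row at switch screening. It points to section 7.1.2.4, which collects disease history, and no switch condition uses it. It is not a bar.

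**Size.** The amendment 03-US.01 rationale gives 233 randomized. With 2:1 allocation the bosutinib arm is about 233 × 1/3 = 77.7, or 78 patients. That is the ceiling on who could ever be considered for the switch, not an estimate of who is affected. The Amendment 3 rationale counted 4 potential switchers, for any kind of failure, by 15-Oct-2018. No T315I rate at bosutinib failure is given, and two figures should not be borrowed for one:

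- The 21 to 33% in section 1.1 covers any mutation that prevents use of specific TKIs.
- The 28 of 141 (28/141 = 19.9%) with T315I in section 1.2.1.2 come from a phase I study that enrolled T315I patients by design.

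**The case against.** The strongest reply is that a known T315I is already covered. Section 7.1.6 is mandatory and specific, the switch is only permitted, and section 2.2 leaves it to the investigator's discretion and the patient's best interest. An investigator would have to overlook both 7.1.6 and 2.3 to dose such a patient. This reduces the likely harm but does not remove the defect: the listed conditions are what the IRT is said to check, and on that list T315I is a ground for entry. The IRT manual may contain a block, but the protocol does not.

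A second reply is that the glossary defines study treatment by what is administered to the patient, so 7.1.6 might stop only the drug being taken when the mutation is found. Section 4.1.1 answers much of this by applying 7.1.6 to asciminib after the switch, and section 2.3 does not depend on the definition.

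Three stronger readings are tempting, but the documents do not support them.

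- **V299L as an equal case.** A reader might infer that V299L must also be barred. Sections 1.2.2 and 2.5 tie V299L only to bosutinib inactivity, and section 1.2.1 says asciminib keeps activity against clinically observed ATP-site resistance mutations. No reason against asciminib in V299L is stated. What remains is that 7.1.2.2 admits it and 7.1.6 stops it.
- **A missing Sanger result as an error.** Late end-of-treatment assessments have a limit, "they must be completed within 42 days (6 weeks) after the bosutinib EOT visit", and the start of asciminib has the same one: "The maximum allowed time frame for patients failing bosutinib to start treatment with asciminib is 42 days after bosutinib EOT". Table 7-2 allows the Sanger sample on the first switch dosing day if it was not taken at end of treatment. A reader might infer that the plan wrongly lets dosing precede the result. But 7.1.2.2 says end-of-treatment assessments are used to judge the switch conditions. Study entry does not require a Sanger result before dosing either: exclusion 1 covers known mutations, the sample is drawn pre-dose on Week 1 Day 1, and only RQ-PCR, marrow and central ECG results must be in hand.
- **Narrowing the mutation criterion to the drug being taken.** A reader might infer this because a mutation resistant only to asciminib could be the ground for giving asciminib. Section 7.1.6 lists the same event as treatment failure, "Detection of new BCR-ABL1 mutations which potentially cause resistance to study treatment (asciminib or bosutinib) at any time after initiation of therapy", and permits the switch, so the two sections agree. Rewording would change mandatory discontinuation and the time-to-treatment-failure events in an ongoing randomized comparison where discontinuation counts as non-response.

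**Conclusion.** The plan is wrong as written for T315I and should be corrected. A stated rule gives a result that sections 7.1.6, 4.1.1 and 2.3 contradict, so this is more than missing detail. For V299L there is an inconsistency to resolve and no demonstrated harm.

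The number of patients affected is small and unquantified, and bounded above by the bosutinib arm. The consequences are for the safety of switched patients and for the switch-phase safety and exploratory efficacy analyses. A reader might infer that the main comparison is at risk. It is not: section 10.4.3 counts anyone who discontinues randomized treatment before Week 24 as a non-responder, section 10.5.1 derives the Week 96 endpoint in the same way, and post-switch responses belong to the exploratory analyses.

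The conclusion assumes that the listed conditions are what sites and the IRT apply, and that no T315I block exists in material not shown.

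**What to change.** 1. Add *T315I mutation detected at any time* to the conditions preventing the switch in 7.1.2.2 and the protocol summary, so that it is among the conditions the IRT checks.
2. Reconcile 7.1.2.2 and 7.1.6 for V299L, either by limiting the V299L stop in 7.1.6 to bosutinib or by adding V299L to the bar. The choice is the sponsor's, and neither should be the default.
3. Optional: review the end-of-treatment Sanger result before the first asciminib dose, within the existing 42 days. This goes beyond the entry standard.

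The cost of items 1 and 2 is a few lines of text and a matching IRT check. Patients with T315I would enter survival follow-up, as 7.1.2.2 already provides for anyone not meeting the conditions. Item 3 needs no new blood draw, since Table 7-3 runs the end-of-treatment Sanger test on the RQ-PCR sample, but it may cause a short wait because turnaround is not stated.

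The change was still worth making at the August 2020 amendment. If recruitment completion on 22-Oct-2019 is taken as the last randomization, the 96-week switch window (96 × 7 = 672 days) runs to about August 2021.

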
Conditions to be fulfilled for asciminib switch
	
1. Failure to bosutinib treatment up to 96 weeks after the last patient received the first dose (adapted from the 2013 ELN Guidelines; Baccarani et al 2013). Patients must meet at least 1 of the following criteria. Failure is defined as follows:
 
 • Three months after the initiation of therapy or thereafter: No CHR or > 95% Ph+ metaphases. • Six months after the initiation of therapy or thereafter: BCR-ABL1 ratio > 10% IS and/or > 65% Ph+ metaphases. • Twelve months after initiation of therapy or thereafter: BCR-ABL1 ratio > 10% IS and/or > 35% Ph+ metaphases. • At any time after the initiation of therapy, loss of CHR, CCyR or PCyR. • At any time after the initiation of therapy, detection of new BCR-ABL1 mutations which potentially cause resistance to study treatment (asciminib or bosutinib). • At any time after the initiation of therapy, confirmed loss of MMR in 2 consecutive tests. • At any time after the initiation of therapy, new clonal chromosome abnormalities in Ph+ cells: CCA/Ph+. 
Conditions preventing patients to switch to asciminib:
 
 • Any Grade 3 or 4 toxicity which has not resolved to Grade 2 or lower within 28 days and before starting asciminib treatment. • Asymptomatic (Grade 2) pancreatitis if not resolved within 28 days • Disease progression while on bosutinib treatment. The following events are considered disease progression: 
 • Accelerated phase (AP) as defined by any of the following: 
 • ≥ 15% blasts in the peripheral blood or bone marrow aspirate, but < 30% blasts in both the peripheral blood and bone marrow aspirate. • ≥ 30% blasts plus promyelocytes in peripheral blood or bone marrow aspirate. • ≥ 20% basophils in the peripheral blood. • Thrombocytopenia (< 100 x 10⁹/L) that is unrelated to therapy. • Blast crisis (BC) as defined by any of the following: 
 • ≥ 30% blasts in peripheral blood or bone marrow aspirate

	
 • Appearance of extramedullary involvement other than hepatosplenomegaly proven by biopsy (i.e., chloroma). • QTcF at time of switch > 480 msec or inability to determine QTc interval
Investigational and reference therapy	Asciminib 40 mg BID Bosutinib 500 mg QD

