1.2.1.2 Clinical experience

Asciminib is undergoing evaluation in a first-in-human (FIH) phase I clinical study, study [CABL001X2101].

This study evaluates patients with 1) CML who have been treated with at least 2 prior TKIs, or 2) who have the T315I mutation and have been treated with at least 1 prior TKI, or 3) who have Acute Lymphoblastic Leukemia (ALL) and have been treated with at least 1 prior TKI. The study evaluates administration of asciminib in a BID single agent dosing schedule, as well as in a QD single agent schedule, and in combination with nilotinib, imatinib, and dasatinib. In the present document, discussion will focus on data from CML patients treated with asciminib BID single agent only.

As of 01-Sep-2017, a total of 239 CML or Ph+ ALL patients have been treated with either single agent oral asciminib or in combination cohorts. 150 CML patients have been treated with asciminib monotherapy. Based on the preliminary efficacy, safety and tolerability in patients with CML-CP or CML-AP treated with asciminib as a single agent on a BID schedule in study [CABL001X2101] and the results of a population PK/PD exposure-response model, the

dose of 40 mg BID has been selected as the recommended dose to be used in future studies in patients with CML-CP who do not harbor T315I mutations.

Efficacy:

Preliminary data from the ongoing Phase I FIH study [CABL001X2101] indicate that asciminib exhibits single-agent activity in patients with CML who have failed at least two prior TKIs or are intolerant to TKIs, as demonstrated by major molecular response and reduction in the BCR-ABL1 % IS. Asciminib has demonstrated anti-tumor activity at doses greater or equal to 10 mg BID as well as daily higher doses.

To date, efficacy data in 141 patients with chronic-phase CML treated with single agent asciminib therapy (10-200 mg BID and 80-200 mg QD) are available (113 patients without T315I mutation and 28 with T315I mutation).

Of the 62 patients with BCR-ABL1 no greater than 10 % IS at screening and without T315I mutation, 1-log reduction of BCRABL1 % IS was achieved in 16 of 62 (25.8%) patients by 6 months and 19 of 62 (30.6%) patients by 12 months. For asciminib 40 mg BID dose, of the 17 patients studied, 1-log reduction of BCRABL1 % IS was achieved in 5 of 17 (29.4%) patients by 6 months, and 12 months.

Please refer to the latest [Asciminib Investigator's Brochure] for more details.

Safety:

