A preliminary population PK-PD model has been developed using data from the [CABL001X2101] study (cut-off 2 May 2016). The time course of molecular response (change in BCR-ABL1 ratio % IS levels from baseline) was described using a semi-physiological model accounting for cell maturation, disease progression and existing resistance. Simulations performed (with 100 patients) using asciminib population PK-PD model revealed that at a dose of 40 mg BID, ~41% (CI₉₅%; 31-51%) of chronic phase CML patients having failed ≥ 2 TKI or intolerant to TKIs are likely to exhibit a 1 log₁₀ reduction of (%) BCR-ABL1 mRNA transcript levels from baseline at 6 months, and 53% (CI₉₅%; 43-63%) at 12 months, and predicting higher probability of achieving BCR-ABL1 mRNA ≥ 1 log reduction at 6 and 12 months with 40 mg BID versus 20 mg BID.

Additional preliminary PK-efficacy and PK-safety analyses to assess the exposure-response relationship for asciminib were conducted ([Section 1.2.1.2](#)). The efficacy measure used was Molecular Response (MR) which is defined as a decline in BCR-ABL1 transcript levels in clinical blood samples of patients with Chronic Myeloid Leukemia (CML). MR was evaluated as both a continuous variable (BCR-ABL1 transcript levels) and categorical variable (whether or not adequate decline in BCR-ABL1 was achieved). The safety measures used were occurrence of Common Toxicity Criteria (CTC) grade 2, 3 or 4 laboratory values for lipase and amylase.

Reviewing the totality of the efficacy, safety, and pharmacokinetic data derived from the [\[CABL001X2101\]](#) study, the recommended dose for asciminib in this phase 3 study is 40 mg BID. Of note, the dose of asciminib single agent BID is further being evaluated in patients with the T315I mutation. At present the recommended dose of 40 mg BID is for patients without the T315I mutation. For this reason, patients with the T315I mutation are excluded from this study.

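### The asciminib switch conditions list no T315I bar, in conflict with the T315I stop in section 7.1.6 and the dose limit in section 2.3

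*Combined protocol and SAP*

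**What the plan says.** Section 7.1.2.2 lets a bosutinib patient switch if at least one failure criterion is met and no preventing condition applies. One criterion is "detection of new BCR-ABL1 mutations which potentially cause resistance to study treatment (asciminib or bosutinib". The preventing conditions are unresolved Grade 3 or 4 toxicity, unresolved asymptomatic Grade 2 pancreatitis, progression to accelerated phase or blast crisis, and QTcF above 480 msec or not determinable. The protocol summary repeats both lists. The conditions are checked through the IRT.

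Section 2.3, on the asciminib dose: "At present the recommended dose of 40 mg BID is for patients without the T315I mutation". It continues: "For this reason, patients with the T315I mutation are excluded from this study". Section 1.2.1.2 gives the same limit, describing 40 mg BID as the "recommended dose to be used in future studies in patients with CML-CP who do not harbor T315I mutations".

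Section 7.1.6, on stopping: "In the event of detection of T315I or V299L mutations at any time the patient" must come off study treatment. A separate bullet in the same list makes treatment failure a mandatory stop too, and adds: "Patients randomized to bosutinib treatment experiencing treatment failure may switch to asciminib treatment". Section 4.1.1 carries the stopping rules into the switch phase: "Discontinuation of asciminib for patients who have switched over from bosutinib must follow the guidelines provided in" section 7.1.6.

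**The concern.** T315I emerging on bosutinib is one of the more predictable ways for that drug to fail, because sections 1.2.2 and 2.5 say bosutinib has no activity against it. The switch list treats a new resistance mutation as a reason to offer asciminib and contains nothing to stop the offer when the mutation is T315I. A site or an IRT check working from that list alone could start a patient on a dose the protocol does not support for T315I, and section 7.1.6 would then require the drug to be stopped.

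The stake is at patient level. One dose of asciminib after bosutinib failure also places the patient in the Switch Analysis Set (section 10.1.6), which serves a secondary safety objective and the exploratory post-switch efficacy analyses.

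**Working it through.** No sample size, power or alpha figure is involved. The check sets the sections against each other.

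1. **Does a new T315I qualify for the switch?** Section 7.1.2.2 lists 7 failure criteria and requires at least 1. The new-mutation criterion is 1 of the 7. Since bosutinib is inactive against T315I, a new T315I satisfies it alone. The entry exclusion in section 5.3 does not help, because it covers only T315I or V299L known before study entry.

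2. **Does any listed bar apply?** There are 4 bars: toxicity, pancreatitis, progression and QTcF. Mutation bars: 0 of 4. Taken alone, the list admits the patient.

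3. **Is there a supported dose?** Sections 2.3 and 1.2.1.2 limit 40 mg BID to patients without T315I, and section 2.3 says the BID dose for T315I is still being evaluated. Section 6.2 forbids escalation above 40 mg BID. The study therefore has no other dose to offer.

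4. **Does section 7.1.6 resolve it?** Three mandatory stops compare as follows.

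| Reason for stop in 7.1.6 | Switch permission in 7.1.6 | Status in the 7.1.2.2 switch list |
|---|---|---|
| Treatment failure | Yes, for bosutinib patients | Qualifies for switch |
| Disease progression | None | Restated as a bar |
| T315I or V299L detected | None | Not mentioned as a bar; a new T315I qualifies as failure |

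Progression was carried into the switch list as a bar and T315I was not. A mandatory stop on bosutinib is also the normal route into the switch, so the T315I stop does not by itself tell a site that asciminib is closed.

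5. **When would T315I be found?** Under section 7.2.1.1, Sanger sequencing is done at Week 1 Day 1, on confirmed loss of MMR and/or at EOT. Sequencing every 12 weeks applies only to patients positive at Week 1 Day 1. For a patient negative then who never reached MMR, EOT is the first scheduled chance to detect T315I. If the EOT test was missed, Table 7-2 places it on S-Week 1 Day 1; Table 7-3 makes that sample pre-dose, but dosing starts the same day. A patient who qualified on another criterion could therefore start asciminib before the result is known. Table 7-2 records mutation status at switch screening, but no listed condition uses it. By contrast, section 7.1.2.4 requires RQ-PCR and marrow results before randomization and first dose; no equivalent sentence covers the Sanger result before the first switch dose.

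6. **How many patients?** The documents give neither an on-study T315I frequency nor a projected switch rate. The ceiling is the planned bosutinib arm, 222 × 1/3 = 74 (section 10.8). If the 233 patients reported as randomized in Amendment 03-US.01 split 2:1, it is 233 / 3 ≈ 78. The only count of switch candidates is 4 as of 15-Oct-2018, in the Amendment 3 rationale. None of these estimates the number affected.

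7. **Does it reach the primary endpoint?** No. Section 10.4.3 counts anyone who discontinues randomized treatment before Week 24 as a non-responder, so what is given afterwards does not change the patient's classification.

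**The case against.** The strongest reply is that section 7.1.6 already bars the switch. Its T315I bullet orders discontinuation of study treatment, and the glossary defines study treatment as any drug in any study arm, which includes asciminib. The treatment-failure bullet adds a switch permission; the T315I bullet does not. Section 2.3 describes T315I patients as excluded from the study, not merely from randomization. On a combined reading, failure may switch and T315I may not. This stands as a fair reading. It means the protocol cannot be said outright to permit the start, though a reader might infer that from section 7.1.2.2 alone. It does not remove the conflict, because section 7.1.2.2 makes no reference to the rule, restates the progression stop and omits this one.

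A second reply is that EOT assessments must be completed and used to judge the switch, with up to 42 days allowed, so the mutation result would normally be available. That covers most cases. It does not cover the sample deferred to S-Week 1 Day 1, or a result still pending at first dose.

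A third is that the IRT manual may contain a mutation check. It is not among the documents, so this can be neither confirmed nor excluded.

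A reader might also infer a toxicity hazard. The documents do not support that. Section 1.2.1.2 reports 28 chronic-phase T315I patients treated with single-agent asciminib across a range of doses, and section 2.3 describes increased toxicity at 80 mg BID and above. They report no added toxicity of 40 mg BID in T315I. The documented problem is that this dose is not supported for T315I.

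**Conclusion.** The concern holds as a conflict between sections. Applied as written, the switch list admits a patient with a new T315I, while section 2.3 does not support the dose and sections 7.1.6 and 4.1.1 require the drug to stop. The late-result gap is separate and real: even on the stricter reading of section 7.1.6, T315I may be found only after asciminib has started.

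The size is unknown and bounded only by the bosutinib arm. The unit of harm is one patient started on an unsupported dose and then stopped, who also enters the Switch Analysis Set. A reader might infer that the randomized comparison is compromised; the Week 24 primary endpoint is not affected.

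The conclusion rests on the protocol text and assumes that no mutation block exists in the unseen IRT manual. It is a modest correction, worth making because it concerns individual dosing and is simple to state.

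**What to change.** Add 'T315I detected at any time (see 7.1.6)' to the conditions preventing a switch in section 7.1.2.2, in the protocol summary and in the IRT switch check. Patients barred this way enter survival follow-up, as section 7.1.2.2 already provides for anyone who does not meet the conditions.

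Require the EOT Sanger result before the first asciminib dose, within the 42-day window. If the EOT sample was missed, take it at switch screening rather than on S-Week 1 Day 1; the footnote to Table 7-3 already allows for collection at that visit.

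The EOT test is already scheduled and runs on the RQ-PCR blood sample (Table 7-3), so it needs no new sample. The costs are a protocol amendment with the approvals in section 12.1 and, for some patients, a wait off therapy for the result. The documents give no laboratory turnaround; the window allows 42 days, or 6 weeks. No analysis changes.

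Narrowing the failure criterion to bosutinib resistance would not help, because T315I would still qualify. A ruling on V299L is not needed to close this point.
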